2.2 STUDY OBJECTIVES

Primary objectives:

1. Explore baseline characteristics and drug utilization patterns of 11 commonly used antidepressant therapy during 90 days of acute treatment phase
 - Top 11 commonly used antidepressants according to local market data are as follows:
 - Escitalopram, paroxetine, fluoxetine, mirtazapine, duloxetine, sertraline, venlafaxine, tianeptine, vortioxetine, desvenlafaxine, bupropion
 - Proportion of antidepressants prescribed by sex, age (<20, 21-64, > 65), sex and age combined
 - Initial doses used, average daily doses of each antidepressants
 - Average length of treatment with index medication before therapy change occurs (switching, combination, augmentation, discontinuation)
 - Adherence and persistence measured by medication possession ratio during first 90 days of treatment period
2. Explore drug utilization patterns such as therapy changes, medication compliance and recurrence relationship, and risk of adverse outcomes during maintenance phase
 - The choice of antidepressant, average length of new treatment maintenance, average number of co-administered medications (e.g., atypical antipsychotics, mood stabilizer, thyroid hormone, psychostimulant) when following changes occur from initial monotherapy:
 - Switching
 - Combination
 - Augmentation
 - Medication compliance and recurrence
 - Compliance measured as adherence and persistence
 - Recurrence
 - Relationship between recurrence and compliance

PFIZER CONFIDENTIAL

- *Risk of adverse outcomes measurement between individual ADs that are well known to be treatment-related (e.g., hyponatremia, GI bleeding, fractures, falls, risk of intracranial hemorrhage, attempted suicide/self-harm, myocardial infarction, epilepsy/seizures, stroke/transient ischemic stroke)*

Secondary objectives:

1. *Choice of antidepressants and drug utilization patterns in patients with various comorbidities*
 - *Psychiatric comorbidities*
 - *Mild cognitive impairment (MCI)*
2. *The relationship of non-pharmacologic treatment and discontinuation, medication compliance*
 - *Non-pharmacologic treatments may include: cognitive behavioral therapy (CBT), frequency of physician visit during acute and maintenance phase of treatment*
 - *Frequency of visit during the first 3 months of acute phase and its relationship to treatment maintenance at 4, 5, 6, 7, 8, 9 month time points and discontinuation rate*
3. *Choice of antidepressants by non-psychiatric specialty*

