7 STATISTICAL METHODOLOGY AND STATISTICAL ANALYSES

7.1 STATISTICAL METHODS

Means, medians, and standard deviations will be provided for continuous variables when performing descriptive analysis of continuous data. Numbers and percentages will be provided for dichotomous and polychotomous variables when performing descriptive analysis of categorical data. Bivariate comparisons of baseline characteristics and outcomes measures will be provided. Appropriate tests (e.g., t-test, chi-square test) will be used based on the distribution of the measure. The cumulative incidence rate for clinical outcomes (major bleeding event, and stroke) will be calculated. The incidence rate will be calculated as the number of patients who experience the event divided by the observed time at risk. An unadjusted Kaplan Meier curve will be drawn to illustrate time-to-event.

PFIZER CONFIDENTIAL

[figure not shown]
The propensity score matching (PSM) technique and the propensity score weighting technique will be used to control for confounders when comparing the antidepressants. After PSM, no significant differences are expected among all pre-index measures between the antidepressant cohorts except for clinical indication differences. Also covariates in Table 3 will be included in multivariate logistic regression framework for each antidepressant choice (binary variable of 1 for choice and 0 for no choice). Covariates will include variables such as age, geographic region, CCI score, and comorbidities. Non-pharmacologic treatments will be used as a covariate if dependent variable is adherence, persistence, or discontinuation since a previous study reported accompanying number of non-pharmacologic treatments significantly increase adherence of antidepressants (Ahn J et al., 2011). The final lists of variables to be used in the model will be discussed and determined during analysis development, after reviewing the pre-matched descriptive tables and post-matched pre-index measures. All data analysis will be executed using statistical software SAS version 9.4 or later.

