7.2.2 Study Drug Analysis in Maintenance Phase

- To understand the top 11 antidepressants usage among the Korean patients with depression in maintenance treatment phase
- Primary analysis
- Endpoints:
 - Choice of study drug
 - Average length of new treatment maintenance
 - Average number of co-medications (e.g., atypical antipsychotics, mood stabilizer, thyroid hormone, psychostimulant) when following changes occur from initial monotherapy: switching, combination, augmentation
 - Medication compliance (adherence, discontinuation, and persistence)
 - Recurrence by each antidepressant, by compliance
 - Risk of adverse events
- Population: patients from the acute treatment phase who started maintenance treatment (after 90 days from the index date)
- Significance on continuous variables will be tested by ANOVA (if equal variance condition satisfied) or Kruskal-Wallis H test (otherwise). Provider specialty and other patient characteristics will be used to fit antidepressant choice by multivariate logistic regression analysis of each study drug choice.
- Covariates: antidepressant class covariates such as SSRIs, SNRIs, and other ADs will be used as grouping variables.
- Missing values will be dropped from the analysis
- The role of this analysis is to provide information on study antidepressants in the maintenance phase of drug therapy for Korean patients with depression.

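### No adjusted analysis is named for recurrence by compliance, part of primary objective 2, so the contrast defaults to a bivariate comparison open to confounding

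*SAP*

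**What the plan says.** SAP section 2.2 lists "Relationship between recurrence and compliance" under primary objective 2, whose parent sentence is "Explore drug utilization patterns such as therapy changes, medication compliance and recurrence relationship, and risk of adverse outcomes during maintenance phase". Protocol section 8 has the same item. SAP 7.2.2, labelled a primary analysis, turns it into one endpoint line: "Recurrence by each antidepressant, by compliance".

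The adjustment methods are in SAP 7.1:

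- Propensity score matching and weighting "will be used to control for confounders when comparing the antidepressants".
- The Table 3 covariates enter a "multivariate logistic regression framework for each antidepressant choice".
- "Non-pharmacologic treatments will be used as a covariate if dependent variable is adherence, persistence, or discontinuation".

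SAP 7.1 also promises bivariate comparisons of outcome measures and an unadjusted Kaplan-Meier curve. SAP 7.2.2 adds ANOVA or Kruskal-Wallis for continuous variables, the drug-choice regression again, and drug class as a grouping variable. Protocol 9.7 uses matched data for comparing the 11 drugs, recurrence included, and time-to-event models for safety outcomes.

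**The concern.** Matching or weighting on index drug makes the drug groups alike. It does nothing to make compliant patients resemble non-compliant ones. Psychiatric comorbidity, earlier service use and type of prescriber can plausibly affect both whether a patient stays on treatment and whether that patient is admitted or seen in an emergency room, which are recurrence events under SAP 5.1.

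The documents themselves recognise determinants of compliance. Protocol 9.4 excludes Medical Aid patients because their compliance may differ, and SAP 7.1 says that non-pharmacologic treatments raise adherence. Those treatments, as listed in Table 3, include electroconvulsive therapy and psychiatric emergency treatment, which are plausible markers of severity. Yet they enter a model only when compliance is the outcome.

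At stake is how one component of a primary objective will be read. Protocol section 7 already presents low adherence as a cause of recurrence in Korea, and protocol 9.7 sets p<0.05 as the mark of significance. A confounded crude difference could easily be taken as support for that belief.

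**Working it through.** The plan gives no power, effect size, recurrence rate or compliance split for this contrast, so there is no figure to reproduce. The check has four parts.

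**1. Scope of each named method**

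| Method | Where | Applies to | Reaches recurrence by compliance? |
|---|---|---|---|
| Propensity matching, weighting | SAP 7.1 | contrasts between drugs | no |
| Multivariate logistic regression | SAP 7.1, 7.2.2 | drug choice as outcome | no |
| Non-pharmacologic covariate rule | SAP 7.1 | adherence, persistence or discontinuation as outcome | no |
| Matched data | Protocol 9.7 | the 11-drug comparison | no |
| Time-to-event models | Protocol 9.7 | safety outcomes | no |
| ANOVA, Kruskal-Wallis | SAP 7.2.2 | continuous variables | no, recurrence is an event |
| Bivariate comparison of outcomes | SAP 7.1 | general | yes, unadjusted |

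**2. Possible size of the confounding (every input assumed)**

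Assume a binary baseline factor in 30% of patients, 50% non-compliance and 10% recurrence where the factor is absent, and no effect of compliance. Let the factor multiply the odds of non-compliance by k and the recurrence risk by g. Let p1 and p0 be its prevalence in non-compliant and compliant patients. Then crude RR = [1 + p1(g − 1)] / [1 + p0(g − 1)].

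- k = g = 1.5: non-compliance with the factor is 0.60. p1 = 0.18/0.53 = 0.340 and p0 = 0.12/0.47 = 0.255. RR = 1.170/1.128 = 1.04.
- k = g = 2: non-compliance with the factor is 0.667. p1 = 0.20/0.55 = 0.364 and p0 = 0.10/0.45 = 0.222. Recurrence is 13.64% v 12.22%, RR 1.12.
- k = g = 3: non-compliance with the factor is 0.75. p1 = 0.225/0.575 = 0.391 and p0 = 0.075/0.425 = 0.176. RR = 1.783/1.353 = 1.32.

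**3. Whether covariates alone would be enough**

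They would not. Under SAP 5.1, augmentation ends persistence and is also recurrence item 6. Periods with an adverse outcome count as non-adherent, and suicide attempt is both an adverse outcome and recurrence item 5. Compliance is measured over up to 180 days, and recurrence can fall in the same window.

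To show the size, let a share a of patients be augmented with a listed drug before day 90, so that they are both non-adherent and recurrent by definition. Let the rest split 50:50 on compliance with 10% recurrence either way, and count all recurrences from the index date. Then RR = {[0.5(1 − a)(0.10) + a] / [0.5(1 − a) + a]} / 0.10.

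- a = 2%: (0.069/0.51)/0.10 = 1.35
- a = 5%: (0.0975/0.525)/0.10 = 1.86
- a = 10%: (0.145/0.55)/0.10 = 2.64

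The shares are assumptions. The built-in association is as large as or larger than the confounding in part 2, and baseline covariates cannot remove it.

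**4. Whether a landmark fits the data**

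The last index date is 30 June 2019, and 180 days later is 27 December 2019. Data run to 31 December 2020, 366 + 4 = 370 days after that. Every index date therefore leaves about a year of data after a day-180 landmark. Data start in January 2017 and indexing in January 2018, so 12 months of pre-index visits are available as well.

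**The case against.** The strongest reply is that the SAP nowhere says this contrast will be unadjusted. A reader might infer that it does, but the documents do not support that: the bivariate default follows from silence on any other method. A reader might also infer that adjustment is confined to drug comparisons and drug choice. That too goes too far, because SAP 7.1 implies adjusted models with adherence, persistence or discontinuation as the outcome. These still do not address recurrence by compliance. SAP 7.1 leaves the final variable lists to analysis development, but for models already named and tied to the matching tables.

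Index drug may be partly handled. The endpoint line can be read as recurrence within each drug, split by compliance; drug class is a grouping variable; and SAP 4.4 allows optional subgroups by age, gender, comorbidities and specialty. This stands as partial mitigation. It does not adjust jointly for comorbidity, prior visits and specialty.

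The objective is exploratory, SAP section 3 sets no hypotheses, and 7.2.2 says that its role is to provide information. This also stands: no confirmatory claim fails, and no passage promises a causal effect of compliance.

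Finally, a reader might infer that a highly significant false finding is assured. Scaling the earlier study's 752,190 patients over five years to an 18-month intake gives 752,190 × 1.5/5 = 225,657, at which the 2-fold case has z = 9.9. But 7.2.2 covers only patients aged 18 to 70 who started maintenance after 90 days, and the documents do not give that number. If 30% of the scaled intake entered, an assumption, the 1.5-fold case falls from z = 3.1 to 3.1 × √0.3 = 1.7, while the 2-fold case remains at 9.9 × √0.3 = 5.4. The z of 9.9 should not be used as the measure of the problem.

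**Conclusion.** The point holds in this form: a relationship named under a primary objective has no adjusted analysis with recurrence as outcome and compliance as exposure. Followed as written, it defaults to a bivariate comparison, possibly within drug or drug class. The null crude RR of 1.04 to 1.32 is an illustration that rests wholly on assumed prevalence, strengths and baseline rates. It shows that moderate confounding could produce a visible association, not that it will. Because the objective is exploratory, the consequence is a confounded association open to misreading. The change should be made, but the study's validity as a whole does not turn on it.

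**What to change.** Add a paragraph to SAP 7.2.2 that specifies:

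- a Cox model, or logistic regression at a fixed horizon, for recurrence with compliance as the exposure;
- compliance fixed before recurrence is counted, for example by a landmark at the end of the 180-day compliance window, or else handled as time-varying;
- adjustment for index drug, age, sex, baseline comorbidities and CCI, prescriber specialty, and pre-index inpatient, outpatient and emergency visits;
- the crude contrast shown beside the adjusted one;
- a sensitivity analysis without recurrence components that also mark non-compliance: augmentation, suicide attempt, and re-prescription after a 30-day drug holiday. A 30-day holiday exceeds the 14-day permitted gap, and one that began before the landmark can become a recurrence only in patients who had already stopped;
- a statement that the result is an association.

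The covariates are in Table 3 or can be built from the same claims, so the extra work is modest. There are two real costs. A landmark drops patients whose recurrence comes before it, so the question becomes recurrence after day 180 among those still free of it. And SAP section 1 records that the SAP was amended during data analysis, so the model must be documented as added after analysis began.

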5.1 EFFICACY/EFFECTIVENESS ENDPOINT(S)

Medication compliance (persistence, discontinuation, adherence) along with recurrence are main primary efficacy endpoints and they are defined as follows:

1. MPR (medication possession ratio)
For each of 11 study drugs, the MPR will be calculated by (Days of medication possession from the prescriptions filled in the 180 days) / (180 days + extra days of drug supply from the last prescription fill during the 180 days)
2. Persistence
For each of 11 study drugs, the average length of treatment on the index drug during the first 180 day period (allowing 14 day permissible gap) will be

PFIZER CONFIDENTIAL

calculated. Switching, combination, augmentation, discontinuation will terminate the persistent period.

3. Discontinuation

For each of 11 study drugs chosen as index drug, the percentage of discontinuation in the first 90 days from the index date (acute treatment phase) will be measured (allowing 14 day permissible gap)

4. Adherence

For each of 11 study drugs chosen as index drug, adherence will be measured by MPR and persistence during the first 90 day and 180 day from the index date, respectively (acute treatment phase). MPR ≥ 0.75 and persistence ≥ 90 will be considered as adherence.

* For those period with any identified adverse outcome such as GI bleeding will be considered as a non-adherent period.

5. Recurrence

Recurrence during the acute treatment phase was operationally defined as either one of the following being satisfied:

- 1) Inpatient episode with a diagnosis code in Table 1
- 2) Inpatient episodes via the department of psychiatry or emergency medicine
- 3) Inpatient episode via nursing hospital
- 4) Emergency room visit with a diagnosis code in Table 1
- 5) Suicide attempt identified by the following KCD-7 codes:
 - T40 Poisoning by narcotics and psychodysleptics [hallucinogens]
 - T41 Poisoning by anaesthetics and therapeutic gases
 - T42 Poisoning by antiepileptic, sedative-hypnotic and antiparkinsonism drugs
 - T43 Poisoning by psychotropic drugs, not elsewhere classified
 - T54 Toxic effect of corrosive substances
 - T60 Toxic effect of pesticides
 - X60-X84 intentional self harm
- 6) Augmentation of the following non-AD drugs
 - Antipsychotic: amisulpride, aripiprazole, olanzapine, quetiapine, risperidone, perphenazine
 - Anticonvulsant: carbamazepine, valproic acid, lamotrigine
 - Mood stabilizer: lithium
 - Anxiolytic: buspirone
 - Thyroid hormone: levothyroxine, liothyronine

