Recurrence after the acute treatment phase was operationally defined as either one of the following being satisfied:

- 1) ~6) the same as above
- 7) AD prescription after 30 days of drug holiday

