Persistence	Primary outcome	HIRA Database	
For each of 11 study drugs, the average length of treatment on the index drug during the first 180 day period (allowing 14 day permissible gap) will be calculated
 
Switching, combination, augmentation, discontinuation will terminate the persistent period

Discontinuation	Primary outcome	HIRA Database	For each of 11 study drugs chosen as index drug, the percentage of discontinuation in the first 90 days from the index date (acute treatment phase) will be measured (allowing 14 day permissible gap)
Adherence	Primary outcome	HIRA Database	
For each of 11 study drugs chosen as index drug, adherence will be measured by MPR and persistence during the first 90 day and 180 day period from the index date, respectively (acute treatment phase). MPR ≥ 0.75 and persistence ≥ 90 will be considered as adherence.
 
* For those period with any identified adverse outcome such as GI bleeding will be considered as non-adherent period

Drug utilization pattern in acute phase	Secondary outcome	HIRA Database	
During the first 90 day period starting from the index date, the following types of drug utilization pattern is recorded
 
- monotherapy (kept on the index medication)- switching (switched to other antidepressant)- combination (adding other antidepressant)- augmentation (adding other non-AD drug such as antipsychotic)
Drug utilization pattern in maintenance phase	Secondary outcome	HIRA Database	
During the second 90 day period (91 ~ 180 days) starting from the index date, the following types of drug utilization pattern is recorded
 
- choice of antidepressant- monotherapy (kept on the same medication)- switching (switched to other antidepressant)- combination (adding other antidepressant)- augmentation (adding other non-AD drug such as antipsychotic)

PFIZER CONFIDENTIAL

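### Recurrence by compliance (SAP 7.2.2): persistence and 180-day MPR overlap in time with recurrence counted from day 91, so a recurrence can lower the compliance it is compared with

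*SAP*

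**What the plan says.** Primary objective 2 (SAP 2.2) includes "Relationship between recurrence and compliance" in the maintenance phase. SAP 7.2.2 carries this out as "Recurrence by each antidepressant, by compliance" and names compliance as adherence, discontinuation and persistence. Its population is patients who go on to maintenance treatment after day 90; being free of recurrence at that point is not a condition.

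The measurement windows are in SAP 5.1 and Table 3 (SAP 5.4):

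- **MPR:** the numerator is "Days of medication possession from the prescriptions filled in the 180 days".
- **Persistence:** "the average length of treatment on the index drug during the first 180 day period". "Switching, combination, augmentation, discontinuation will terminate the persistent period".
- **Discontinuation:** "the percentage of discontinuation in the first 90 days from the index date (acute treatment phase) will be measured".
- **Adherence:** the text pairs MPR and persistence with 90 and 180 days, in that order, and labels the whole as acute phase. The cut-offs are MPR of at least 0.75 and persistence of at least 90.
- **Recurrence:** there is one definition for the acute phase and one for afterwards ("Recurrence after the acute treatment phase was operationally defined as either one of the following being satisfied"). Both include augmentation with listed non-antidepressant drugs (item 6). The later one adds an antidepressant prescription after a 30-day drug holiday (item 7). No end day is given.

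**The concern.** To ask whether poor compliance is followed by recurrence, compliance has to be known before the recurrence happens. Here a patient admitted on day 95 is still being classified by drug supply up to day 180. If the admission leads to a switch or stop of the index drug, supply and persistence fall because of the recurrence. The table then shows more recurrence among the less compliant even if compliance has no effect.

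The plan has no landmark, no time-varying compliance and no cut-off of compliance at recurrence. The propensity methods in SAP 7.1 are for comparing antidepressants, and the protocol (9.7) specifies time-to-event models for safety outcomes. Adjusting for confounders would not repair the time order in any case. At stake is one component of a primary objective, on a question where the protocol's rationale already presents adherence as a major influence on recurrence.

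**Working it through.** The plan gives no recurrence rate, effect size or event count for this analysis, so there is no stated figure to reproduce.

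**1. Which compliance measures can a recurrence from day 91 change?**

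| Measure | Window in the SAP | Can it change? |
|---|---|---|
| Persistence length | to day 180 | Yes |
| MPR as defined in 5.1 item 1 | to day 180 | Yes, if index-drug supply falls |
| Adherence flag with 180-day MPR | to day 180 | Yes |
| Adherence flag with 90-day MPR | essentially fixed by day 90 | No |
| Discontinuation | to day 90 | No |

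In the fourth row the persistence cut-off is 90 days, so a change of drug after day 90 cannot fail it.

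**2. Links that are built in.** Augmentation (item 6) is a recurrence and also ends persistence; it need not alter index-drug MPR. Suicide attempt is a recurrence criterion and also an adverse outcome (SAP 5.2), and 5.1 treats adverse-outcome periods as non-adherent. Item 7 works the other way: a 30-day holiday exceeds the 14-day permissible gap, so non-compliance is part of that recurrence.

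**3. The 180-day MPR cut-off.** Ignoring the extra-days term, 0.75 × 180 = 135 days of supply. A fully supplied patient whose index drug ends at a recurrence has MPR 91/180 = 0.51 on day 91, 120/180 = 0.67 on day 120 and 134/180 = 0.74 on day 134. All three become non-adherent.

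**4. False risk ratio for a flag using 180-day MPR.** Assumptions, none from the documents: no true effect; recurrence p = 10%; half of patients otherwise adherent with full supply; a share q of recurrences ends the index drug; recurrence times uniform. Let f be the share of recurrences before day 135 and x = q·f. Then

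- risk in non-adherent = p(1 + x)/(1 + p·x)
- risk in adherent = p(1 − x)/(1 − p·x)
- RR = the first divided by the second

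Recurrence on days 91-180: f = (135 − 91)/(180 − 91) = 44/89 = 0.494.

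Recurrence on days 91-550: f = 44/(550 − 91) = 44/459 = 0.096. Day 550 is the last day available to every patient: 30 Jun 2019 to 31 Dec 2020 is 184 + 366 = 550 days.

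| q | x, days 91-180 | RR | x, days 91-550 | RR |
|---|---|---|---|---|
| 20% | 0.099 | 0.1088/0.0910 = 1.20 | 0.019 | 0.1017/0.0983 = 1.04 (1.035 unrounded) |
| 50% | 0.247 | 0.1217/0.0772 = 1.58 | 0.048 | 0.1043/0.0957 = 1.09 |
| 100% | 0.494 | 0.1424/0.0532 = 2.68 | 0.096 | 0.1086/0.0913 = 1.19 |

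**5. A second set of assumptions.** A null simulation (2,000,000 patients per scenario) used exponential times, 5%, 10% or 20% recurrence by day 180, and 50% spontaneous stopping by day 180. With the 180-day flag, in patients still on drug after day 90, it gave RRs for recurrence on days 91-180 of 1.78-1.89, 2.73-2.99 and 5.60-6.85 when 25%, 50% and 100% of recurrences ended the drug. A landmark at day 90, applied to all patients recurrence-free by then, returned 1.00-1.02 in all nine scenarios. Item 7 was not simulated.

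**6. Room for a later landmark.** 30 Jun 2019 + 180 days = 27 Dec 2019, which leaves 4 + 366 = 370 days to 31 Dec 2020.

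**The case against.** The strongest reply is that the SAP can be read so that much of the problem disappears. MPR is not itself in the list of compliance measures in 7.2.2. If the adherence item means a 90-day MPR, the flag is essentially settled by day 90, as is discontinuation, and only persistence length stays exposed. That is a fair reading, and on it the risk ratios in steps 4 and 5 do not apply to the flag. But MPR is defined in 5.1 only over 180 days, and the SAP's list of changes records a deliberate move to 180, so the text does not settle the matter. Persistence overlaps under either reading.

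Three further points stand:

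- A reader might infer that recurrence is counted from day 0 here. An acute-phase definition exists, but 7.2.2 is the maintenance analysis and does not say that it uses it.
- The size depends on the recurrence window. With a long window most recurrences come too late to affect a 180-day measure. Front-loaded recurrence would move the result towards the larger figures.
- The study design figure is not visible in the text and may show a follow-up period.

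The objective is exploratory and the SAP states no hypotheses. That limits what may be claimed from the table, but does not remove the distortion from it.

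**Conclusion.** The concern holds for persistence length and for 180-day MPR. It holds for the adherence flag, with recurrence from day 91, only if the flag uses the 180-day MPR. It does not hold for discontinuation with recurrence from day 91.

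Under the step 4 assumptions the false risk ratio for a 180-day flag runs from 1.04 to 2.68, depending on how often a recurrence ends the index drug and how long recurrence is counted. The documents supply neither figure.

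A reader might go further and infer that all compliance here is measured after the outcome, or that a risk ratio near 2.7 is to be expected. The documents support neither: the windows overlap in part, and 2.68 requires every recurrence to fall on days 91-180 and to end the index drug. What they do support is that nothing in the text puts compliance before recurrence, so the table can show an association where none exists.

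**What to change.** Put a landmark into SAP 7.2.2, in one of two forms:

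1. Classify compliance from days 0-90 only, in patients free of recurrence to day 90, and count recurrence from day 91 over a stated fixed window.
2. Keep 180-day compliance, but pair it only with recurrence from day 181 over a fixed window, in patients free of recurrence to day 180. At least 370 days of data remain for every patient.

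In either form, count item 7 only when the 30-day holiday begins after the landmark; otherwise a holiday straddling it ties the two measures together again. Reconcile the adherence item with the MPR definition, so that one stated MPR window defines the flag and ends no later than the landmark. State which recurrence definition 7.2.2 uses and the day on which counting ends.

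The cost is SAP wording and one re-run. Patients who recur before the landmark drop out of this one analysis, so the result describes those still recurrence-free at that point.

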9.7. Data analysis

The proportions and drug utilization patterns comparisons of 11 study drugs will use all the patients satisfying inclusion and exclusion criteria (raw data). Adherence, persistence, discontinuation, recurrence, and adverse outcomes comparison of 11 study drugs will use both raw data and matched data where patients will be matched on demographic and clinical characteristics. All outcome variables will be summarized *descriptively* through the tabular and graphical display of mean values, medians, ranges and standard deviations of continuous variables of interest and frequency distributions of categorical variables. Safety outcomes of treatments will be estimated from time-to-event models. The 95% confidence intervals for the estimates will be calculated and $p < 0.05$ will be considered significant. All analyses will be carried out using SAS version 9.4 which is installed on HIRA server. Analysis and reporting will be compliant with Strengthening the Reporting of Observational Studies in Epidemiology (STROBE) recommendations.

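### SAP 7.2 lists by-drug discontinuation, recurrence and adverse outcomes only for patients who reach maintenance, so the 90-day and acute-phase endpoints have no all-patient analysis

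*SAP*

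**What the plan says.** **Endpoints.** SAP 5.1 states that "Medication compliance (persistence, discontinuation, adherence) along with recurrence are main primary efficacy endpoints". For each index drug, "the percentage of discontinuation in the first 90 days from the index date (acute treatment phase) will be measured". Recurrence has two definitions. One begins "Recurrence during the acute treatment phase was operationally defined as either one of the following being satisfied" and has six criteria. The other applies after the acute phase and adds a seventh, "AD prescription after 30 days of drug holiday". SAP 5.2 makes adverse outcomes primary and counts claims after the index date; SAP 4.2 equates the safety set with the full analysis set.

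**Comparison population.** Protocol 9.7 says "Adherence, persistence, discontinuation, recurrence, and adverse outcomes comparison of 11 study drugs will use both raw data and matched data". The same paragraph identifies raw data as "all the patients satisfying inclusion and exclusion criteria (raw data").

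**Listed analyses.** SAP 7.2.1 is the primary acute-phase analysis in everyone meeting the SAP 4.1 criteria, by index drug. SAP 7.2.2 is the primary maintenance-phase analysis. It lists compliance (including discontinuation), recurrence by drug and by compliance, and risk of adverse events. Its population line is "Population: patients from the acute treatment phase who started maintenance treatment (after 90 days from the index date").

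**Specialty analysis.** Secondary objective 3 (SAP 2.2) concerns drug choice by non-psychiatric specialty and carries no comorbidity condition. The population line of SAP 7.2.5 nevertheless requires a prespecified comorbidity, and its role line describes results by comorbidity group.

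**The concern.** A primary endpoint measured over the first 90 days needs a population that starts on day 1. The only place where 7.2 lists discontinuation by drug has a population that starts after day 90. The same holds for recurrence, although the SAP wrote a definition specifically for the acute phase, and for adverse outcomes, although the SAP counts them from the index date.

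A programmer working from 7.2 alone could deliver every listed table and still not produce the 90-day discontinuation percentage or acute-phase recurrence by drug in all initiators. Events in patients who stop early and never enter maintenance would appear in no by-drug table. Propensity matching on pre-index measures (SAP 7.1) does not restore patients removed by what happened after the index date.

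SAP 7.2.5 has a different problem. As written, it answers the specialty question only in patients with a prespecified comorbidity.

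**Working it through.** The plan gives no discontinuation rate, event count or sample size for this point, so there is no figure to reproduce. The check sets the lists side by side.

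| SAP section | Population | Discontinuation | Recurrence | Adverse outcomes |
|---|---|---|---|---|
| 7.2.1 (primary) | All eligible, by index drug | Only as one of four events ending time on the index drug | Not listed | Not listed |
| 7.2.2 (primary) | Entered maintenance after day 90 | Listed | Listed | Listed |
| 7.2.3 (secondary) | Acute-phase population with a comorbidity | Not listed | Not listed | Not listed |
| 7.2.4 (secondary) | Acute-phase population | By number of non-pharmacological treatments, grouped by drug class | Not listed | Not listed |
| 7.2.5 (secondary) | Acute-phase population with a comorbidity | Not listed | Not listed | Not listed |

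**Step 1. What is required.** SAP 5.1 supplies the windows (first 90 days; acute phase) but names no population. Protocol 9.7 supplies the population (all eligible, and matched) but names no window. The all-patient 90-day comparison comes from reading the two together; no single passage states both.

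**Step 2. Can 7.2.1 stand in?** No. Time on the index drug also ends at a switch, combination or augmentation, so the percentage discontinuing cannot be recovered from it. Adherence combines MPR with that same persistence measure.

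**Step 3. Who enters 7.2.2?** I found no rule in the text. SAP Table 3 gives a window for utilization patterns (days 91 to 180), not an entry condition. The endpoint "Average length of new treatment maintenance" and the drug-holiday criterion suggest that switchers and some restarters are in scope, but nothing says so.

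**Step 4. What 7.2.2 would give under each reading.** Let d be the true 90-day discontinuation proportion in all eligible patients and r the share of early stoppers who enter 7.2.2. Assume that everyone who did not stop enters. The observed proportion is

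d_obs = d·r / (d·r + 1 − d).

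- Early stoppers excluded (r = 0): d_obs = 0 / (1 − d) = 0% for every drug, for any d below 1.
- Everyone enters (r = 1): d_obs = d, with no bias.
- Some enter (0 < r < 1): d_obs is below d (for 0 < d < 1). With purely assumed rates of 50% and 30% and r = 0.5, the results are 0.25/0.75 = 33.3% and 0.15/0.85 = 17.6%, a gap of 15.7 points instead of 20. With r = 0.25 they are 0.125/0.625 = 20.0% and 0.075/0.775 = 9.7%, a gap of 10.3 points.
- Discontinuation in 7.2.2 means stopping during maintenance: the formula does not apply, and the 90-day percentage is not listed anywhere by drug.

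The values of d and r are not in the documents. The figures in the third bullet show the mechanism only.

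**Step 5. SAP 7.2.5.** Its population line carries the same comorbidity restriction as 7.2.3, and its role line closely repeats that of 7.2.3. Neither fits secondary objective 3.

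**The case against.** The strongest reply is that the endpoints are not lost. SAP 5.1 and Table 3 say that 90-day discontinuation will be measured for each index drug. SAP 7.1 promises bivariate comparisons of outcomes, applies matching and weighting when comparing the drugs, and treats discontinuation as a dependent variable, without restriction to maintenance patients. On this view 7.2.1 merely has an incomplete list. Primary objective 2 also places compliance, recurrence and adverse outcomes in the maintenance phase, so 7.2.1 and 7.2.2 follow the objectives as written, and the study is exploratory with no hypotheses.

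Much of this stands. It is a reason to keep 7.2.2 and to regard the gap as one of specification. It does not close the gap: SAP 7.1 names no window or population for these comparisons, and the one by-drug listing that does name a population names the restricted one. Objective 2 does not account for a 90-day measure, an acute-phase definition or adverse outcomes counted from the index date.

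A reader might infer that the primary drug comparison will be biased, perhaps even reversed, by selection at day 90. The documents do not support that. Discontinuation in a section on the maintenance phase most naturally means stopping during maintenance, and then there is no biased 90-day figure, only an absent one. The entry condition can also be read as purely time-based, which brings little or no bias. Figure 1 is not shown in the copies reviewed and might bear on how the phases are defined.

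**Conclusion.** The point holds as a mismatch between endpoints and listed analyses. Followed literally, SAP 7.2 omits two things that SAP 5.1 and Protocol 9.7 jointly call for: 90-day discontinuation and acute-phase recurrence by index drug in all eligible patients. It also leaves out of any by-drug table the adverse outcomes of patients who never reach maintenance, although for these the conflict with SAP 4.2 and 5.2 is tempered by objective 2.

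No size can be put on any bias, because the documents give neither early discontinuation rates nor an entry rule. The one result that needs no assumed rate is conditional: 0% for every drug if the 90-day measure were taken in 7.2.2 with early stoppers excluded. The conclusion rests on reading SAP 5.1 and Protocol 9.7 together, and that inference is firmer for discontinuation than for recurrence, since Protocol Table 3 defines recurrence without an acute-phase window.

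The comorbidity restriction in SAP 7.2.5 is a separate error, apparently carried over from 7.2.3, and it lends no support to the main point.

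**What to change.** 1. In SAP 7.2.1, add 90-day discontinuation percentage, acute-phase recurrence and adverse outcomes from the index date, each by index drug in the full analysis set, in raw and matched data as Protocol 9.7 provides.
2. Keep SAP 7.2.2, which serves objective 2, for outcomes after day 90 only. State who enters (how early stoppers, switchers and restarters are handled) and what discontinuation means there. Labelling its results as conditional on entry and reporting non-entrants by drug would be good practice, though no section requires it.
3. In SAP 7.2.5, delete the prespecified-comorbidity condition from the population line and reword the role line to refer to provider specialty.

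The cost is SAP wording and a few extra tables from data already requested. The downside is that each additional table must pass HIRA's privacy check before export from its server (Protocol 9.6).
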